1.1 Eligibility Criteria (Inclusion and Exclusion Criteria)

Subjects considered for enrollment must demonstrate eligibility as outlined in the Study Eligibility Criteria Table (**Table 2**) through a review of the Subject's documented medical history and protocol-driven tests and procedures as outlined in **Table 1**.

Documented evidence of eligibility is required and must be housed with the Subject's study records.

Per the standard definition of rhinitis and for the purposes of this study, Subjects are enrolled if they are experiencing long term chronic rhinitis. Subjects must be experiencing symptoms of rhinitis for at least 6 months to be considered for enrollment defined as:

- Rhinorrhea, anterior runny nose
- AND
- Congestion, blockage (stuffy nose, obstruction)

Table 2: Study Eligibility Criteria

ID:	INCLUSION CRITERIA – Subject must meet all of the following to be enrolled.
I-A	Subject provides written informed consent, including authorization to release health information.
I-B	Subject is 18 years of age or older at the time of consent.
I-C	Subject has provided a negative pregnancy test (if Subject is a woman of childbearing potential (WOCBP).
I-D	Subject WOCBP must be practicing and willing to continue an effective method of birth control during the course of the study.
I-E	Confirmation of moderate to severe symptoms of rhinorrhea. (VAS NSS score for runny nose ≥ 5.0 and rTNSS score for runny nose ≥ 2)
I-F	Confirmation of mild to severe symptoms of nasal congestion. (VAS NSS score ≥ 2.5 for stuffy nose (congestion) and rTNSS score of ≥ 1)
I-G	Confirmation that the total combined VAS NSS score is ≥ 10 for nasal congestion and runny nose.
I-H	Subjects stated willingness to comply with all study procedures, post- treatment care and availability for the duration of the study follow up of 1 year.
I-I	Subject tests negative for active COVID-19 at the start of study screening and continues to be free from COVID-19 symptoms until the time of enrollment/treatment.
I-J	Subject understands and agrees to follow local COVID-19 restrictions (social distancing, face mask, etc.)
I-K	Nasal anatomy appropriate to receive the NEUROMARK™ System.
I-L	Subject is experiencing long term chronic rhinitis. Subject has been experiencing symptoms of rhinitis for at least 6 months prior to enrollment, defined as: rhinorrhea, anterior runny nose AND congestion, blockage (stuffy nose, obstruction).
ID:	EXCLUSION CRITERIA – Subject meeting any of the following to be excluded.
E-A	Subject has clinically significant anatomic obstruction that limits access to the posterior nose as determined by the Study Investigator such as severe septal deviation, prior surgical considerations, cleft palate, nasal polyps, or sino-nasal tumor.
E-B	Subject has an active nasal or sinus infection at the time of treatment.

E-C	Subject has a diagnosis of Atrophic Rhinitis.
E-D	Subject has a Lund-Mackay score >3 during the screening phase, an active history of chronic sinusitis (within the last year).
E-E	Subject has a septal perforation or nasal mucosal erosion/ulceration.
E-F	Subject experiences numbness of the soft palate, excessive dry eye, excessive dry nose, or other indication of neuro/nerve compromise in the sino-nasal anatomy.
E-G	Subject has had prior sinus or nasal surgery that may prevent access or proper placement of the NEUROMARK™ System.
E-H	Subject has had prior head or neck irradiation (head/neck cancer therapy).
E-I	Subject has an allergy or intolerance to anaesthetic agent or other study-required materials.
E-J	Subject is taking anticoagulant medication or 325 mg aspirin that cannot be discontinued before the procedure and for the length of the study.
E-K	Subject has a history of nasal manifestation of rheumatic disease.
E-L	Subject has started a new sino-nasal medication regimen within 4 weeks prior to treatment (i.e. antihistamines, cromolyn, leukotriene receptor antagonists, inhaled or systemic steroids, anticholinergics, expectorants, decongestants) that, per the manufacturer's labelling, has not yet stabilized.
E-M	Subject has uncontrolled Hypothyroidism.
E-N	Subject has uncontrolled Hypertension (stage 2 or higher).
E-O	Subject is an active smoker or has been a smoker within the last 6 months (patient reported).
E-P	Any physical condition that in the Investigator's opinion would prevent adequate study participation or pose increased risk to the study Subject.
E-Q	Subject is pregnant, nursing or plans to become pregnant during the study, or is a WOCBP, but is not willing to use an effective method of birth control.
E-R	Patient is enrolled in an investigational drug or device study or has participated in such a study within the last 30 days prior to screening that in the opinion of the Investigator would interfere with the study results
E-S	Patient presents with any condition or situation which, in the Investigator's opinion, puts the Subject at risk, could confound the study results, or may interfere significantly with the Subject's participation in the study.
E-T	Subject presents with acute sinusitis at time of treatment or other sino-nasal related illness other than rhinitis.
E-U	Subject has history of chronic epistaxis or nosebleed episodes within the last 12 months
E-V	Subject has rhinitis symptoms due to seasonal allergies only.
E-W	Subject has received previous procedure or surgery for chronic rhinitis and/or to disrupt the posterior nasal nerve

2 INTRODUCTION AND BACKGROUND

The NEUROMARK™ System has been developed by Neurent Medical for the treatment of chronic rhinitis through the application of radio frequency (RF) current to disrupt the parasympathetic nerve supply to the nasal cavity. The device consists of a handheld therapeutic device which will be introduced into the nasal cavity under local anesthetic to access the treatment area. In clinical use, the device will be connected to a RF Console which will provide controlled delivery of energy to the treatment tip.

2.1 Clinical Background

Rhinitis refers to inflammation of nasal mucosa, the tissue that lines the nasal cavity. This inflammation can cause nasal congestion, nasal discharge (rhinorrhea), sneezing, postnasal drainage, and numerous other symptoms adversely affecting quality of life.

There are two types of Rhinitis, Allergic Rhinitis (AR) and Nonallergic Rhinitis (NAR). AR is triggered by an allergen, such as pollen or dust. The cause for NAR is not always known, however some common causes are viral infections such as a cold or flu, or environmental irritants such as smoke or chemical fumes. Rhinitis is reported to affect 30% of the population, 21% suffering from AR and 7% from NAR. It is the most common chronic disease in children and also the fifth most common chronic disease in the United States (US) overall.

Inferior turbinate hypertrophy is the main anatomic cause of nasal obstruction and rhinitis is the main non-infectious cause of turbinate hypertrophy. Nasal turbinates are structures located within the nasal cavity (Figure 1). They are made of bone and are covered by soft tissue (mucosa). Their function is to regulate airflow and humidify the air you breathe in through your nasal passages. In patients with Rhinitis, these turbinates swell, leading to nasal congestion and secretion (**Figure 2**).

Treatment options for Rhinitis include medications such as systemic or topical antihistamines, topical corticosteroids, decongestants, anticholinergics, mast cell stabilizers, leukotriene receptor antagonists, and nasal saline. Rhinitis can also be treated with immunotherapy, commonly referred to as the allergy shot. Allergen avoidance can also help to prevent Rhinitis.

In more severe cases, where allergen avoidance, medication, or immunotherapy failed, or are not an option, Rhinitis may be treated surgically by inferior turbinate reduction. This is a surgery in which the turbinate size is permanently reduced. There are two

[figure not shown]

Figure 1: Nasal cavity

[figure not shown]

Figure 2: Nasal cavity with inflamed turbinates

modern surgical options: the delivery of thermal energy to the inflamed soft tissue, resulting in the temporary volumetric reduction of the tissue to improve nasal airflow; and microdebrider resection of the inflamed soft tissue, which has a higher degree of efficacy however requires general anesthetic and is associated with a higher degree of complications.

Research has shown of another potentially effective surgical technique, posterior nasal neurectomy. Vidian neurectomy surgical procedure is a base of skull procedure that severs neural pathways to the eye, mouth and the nose. It is an imbalance in this neural pathway that initiates the inflammatory cascade in effected rhinitis patients and is responsible for mucus production and submucosal engorgement that routinely manifest as congestion and rhinorrhea. A number of published studies have concluded that vidian neurectomy procedures show significant improvement on patient outcomes reported over traditional turbinate surgical interventions at a three-year time point which, in turn, have as significant an improvement over those treated with medical therapy.

2.2 Neurent Medical's Solution

Neurent Medical has developed a novel device-based therapy to treat Rhinitis that leverages the well-published efficacy and durability of vidian neurectomy surgical procedures. The Neurent Medical device aims to treat Rhinitis through localized application of radiofrequency (RF) thermal energy in the nasal cavity to disrupt the parasympathetic nerve supply. Using this method, Neurent Medical envisages that the efficacy of vidian neurectomy can be achieved in an office setting without the associated side effects caused by the transection of the ocular as well as the nasal parasympathetic nerves during a vidian neurectomy procedure. The design of the Neurent Medical device is described in **Section 3**.

3 DEVICE DESCRIPTION

Neurent Medical has received regulatory clearance for the NEUROMARK™ System in the USA under an FDA Class II device designation. The NEUROMARK System used in this clinical investigation is identical to the NEUROMARK System cleared by FDA. The NEUROMARK™ System comprises 2 key elements which are described in this section:

1. The NEUROMARK™ device and
2. The NEUROMARK™ RF Console

3.1 NEUROMARK™ Device

The NEUROMARK™ device comprises a handle, shaft and treatment tip. The treatment tip, which is referred to as the end effector (EE), consists of an array of micro electrodes. These electrodes deliver bipolar RF energy whilst monitoring and providing feedback on the tissue bio-impedance changes to tailor the optimal RF energy level delivery. The shaft of the device is pre-shaped for optimal access and delivery to the nasal cavity. The outer sheath of the shaft constrains and protects the EE during delivery. The NEUROMARK™ device is operated via an ergonomically designed handle, slider and activation button. Once in position within the nasal cavity, the operator engages and moves the slider proximally which retracts the outer sheath, thus deploying the EE.

The NEUROMARK™ device (**Figure 3**) is connected, via a flexible cable, to the NEUROMARK™ RF Console (**Section 3.2**).

[figure not shown]

Figure 3: NEUROMARK™ Device

3.2 NEUROMARK™ RF Console

The NEUROMARK™ Console delivers, monitors and controls RF energy to the device.

The NEUROMARK™ Console algorithm ensures a controlled delivery of RF energy to the EE. The NEUROMARK™ System monitors the tissue properties during the procedure and the algorithm controls the location of the energy delivery, the power delivered and the duration of energy delivery. In doing so, the algorithm will direct energy to the EE electrodes that require energy while restricting energy delivery to EE electrodes that have reached the desired endpoint state change, thus minimizing collateral damage. The algorithm is designed to deliver and control power to the device EE in a specific manner to create micro lesions that penetrate the mucosal tissue to disrupt the nerves.

The Console is mounted on an ergonomic mobile stand for ease of use. The Graphical User Interface (GUI) (**Figure 4**), the interface between the device and the user, is designed to ensure simplicity and control during procedure. The GUI will provide operational instructions for the procedure; directs user to select which nasal cavity to treat, indicates when the device is primed to start treatment, provides status of therapy and indicates when the procedure is complete.

Figure 4: RF Console/Graphical Operator Interface

3.3 Device Operation

The device will be connected to the Console via a flexible electrical cable. The patient will sit in the surgery chair and local anesthetic is administered. The device is inserted into the nasal cavity under endoscopic guidance. For this part of the procedure, the end effector is constrained with only the shaft of the device tracking to the target position (**Figure 5**).

[figure not shown]

Figure 5: Introduction of the device into the nasal cavity - the end effector is not yet deployed.

Under endoscopic guidance, the physician will advance the device towards the posterior superior/inferior region of the nasal cavity. The visual shaft markings on the top and bottom of device shaft are aligned to ensure superior orientation within the nasal cavity during delivery. The physician will align the inter stage marker on the shaft at the lateral attachment of the middle turbinate thus ensuring that the device is correctly positioned prior to initiating deployment of the end effector (see **Figure 6**)

[figure not shown]

Figure 6: Device positioned in the correct target position prior to deployment of the end effector

Once in position, with the surgical landmark of the lateral attachment of the middle turbinate, the physician will move the slider proximally on the handle to the deployed position, thereby deploying the end effector in the nasal cavity (Figure 7: Device in position with end effector deployed. **Figure 7**).

[figure not shown]

Figure 7: Device in position with end effector deployed.

Once the end effector is deployed, and positioning within the cavity is correct, the electrical activation button on the device handle is pressed to assess the tissue bio-impedance. This impedance check provides confirmation of apposition of the electrodes against the lateral wall.

Upon completion of the impedance check, the NEUROMARK™ Console GUI will confirm to the user that they can initiate treatment. To deliver the therapy, the NEUROMARK™ device is activated by pressing down and holding the activation switch on the handle for 2 seconds. Radiofrequency energy will be delivered through the electrodes to create micro-lesions (**Figure 8**).

[figure not shown]

Figure 8: Energy delivery and lesion creation

Energy delivery is algorithmically controlled by the Console based on bioimpedance from the tissue. Once the bioimpedance threshold has been reached the system will automatically stop delivery of energy to that location. The GUI will provide real-time feedback on the progress of the therapy alerting the physician once the therapy has been completed.

Refer to the Investigator's Brochure and the Instructions for Use (IFU) document provided as **Appendix A** and **Appendix B**, respectively, for additional device and device-use details.

4 SUBJECT SCREENING AND ENROLLMENT

4.1 Subject Population

Male or female subjects in good general health who experience chronic rhinitis and meet the study's eligibility criteria as outlined in **Section 1.1, Table 2** will be considered for study participation. Existing medical records may be reviewed to assess the patient for potential eligibility. Subjects whose records support potential eligibility may be approached regarding the study and, if interested, the potential subject will be asked to provide written informed consent before protocol-driven evaluations commence.

4.2 Eligibility Criteria (Inclusion and Exclusion Criteria)

Subjects considered for enrollment must demonstrate eligibility as outlined in the CLARITY Study Eligibility Criteria Table (**Table 2**) through a review of the Subject's documented medical history and protocol-driven tests and procedures as outlined in Study Related Tests, Procedures, and Activities Table (**Table 1**) and further discussed in **Section 4.6**.

Documented evidence of eligibility is required and must be housed with the Subject's study records.

4.3 Subject Recruitment

This study may recruit subjects through in-office, online or other advertising and through existing clients or patients. Any advertising materials to be utilized must be approved by the governing IRB prior to use.

4.4 Subject Reimbursement

Subjects will be compensated for their time and contribution. Compensation is intended to cover any costs associated with travel or other related expenses as well as the Subject's time and contribution. Details concerning reimbursement will be outlined in the site-specific informed consent document, which will undergo IRB/EC review and approval.

4.5 Informed Consent

The Investigator or a designated member of his/her staff should approach the patient to obtain written informed consent. Non-technical language shall be used that is understandable to the Subject. The background of the proposed study and the benefits and risks of the procedures and study will be explained to the Subject. The Subject will be given the plain language study-specific Informed Consent Form (ICF) (example provided as **Appendix C**) which describes all aspects that are relevant to participation. The Subject must sign the consent form prior to study-driven tests or procedures are performed. The informed consent may be provided in hard copy or electronic format. This form or a modification of it must have prior approval of the reviewing IRB or Ethics Committee.

The Subjects and the authorized study personnel obtaining informed consent must sign and date the ICF. A copy must be given to the Subject.

Written informed consent must be obtained prior to performing any protocol-driven tests or procedures.

Once written consent has been obtained, the Subject will be entered on a site-specific screening log. All Subjects *who provide written informed consent* will be entered on the screening log regardless of whether they are enrolled in the study.

As appropriate, important, and new information will be provided to subjects throughout the duration of the study.

It is not expected that a legally authorized representative will provide consent on behalf of study Subject since the Subject must be able to provide active feedback on Quality of Life measures. In addition, this is not an emergent procedure.

If a Subject is unable to read or write, consent shall be obtained through a supervised oral process. The consent process will be appropriately documented.

4.6 Subject Screening

4.6.1 Initial Screening

Prior to obtaining written informed consent, the Subject's existing medical (or other clinic) records may be reviewed by the research staff to determine whether the Subject may be an acceptable candidate for the CLARITY Study. If, upon initial review, there is nothing to indicate that the Subject may not be eligible, the Subject may be approached regarding the study and the informed-consent process may commence.

4.6.2 Active Screening

At any time after the Subject has signed the necessary consent document, but before the NEUROMARK™ procedure subjects will perform eligibility assessments as outlined in **Table 1**. For additional details on the procedures below please refer to the Testing and Evaluation Guidelines document (**Appendix F**) The following must be completed at screening to assess subject eligibility:

- Collect and review medical history, demographics, and concomitant medications.
- Administer Baseline VAS NSS, rTNSS, mini-RQLQ.
- COVID-19 test for active infection.
- Pregnancy test for women of childbearing potential.
- Physical exam (height, weight, blood pressure, respiratory rate, heart rate and temperature).
- Evaluation of the nasal cavity by endoscopic assessment (recorded) to evaluate that the subject is an appropriate candidate for the NEUROMARK™ procedure. A Lund-Kennedy score should be assigned to each nostril.

If the results of the following assessment performed within 6 months prior to treatment are not in the subject's medical record, it must be collected as part of screening:

- Collection and/or review of CT scan of the paranasal sinuses. A Lund-Mackay Score should be assigned to each of the 12 sinuses. The sum of all scores is the Lund-Mackay Score.

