Study Endpoints:	
Safety will be evaluated based on frequency of Serious Adverse Events (SAEs) directly attributable to the NEUROMARK™ System at one (1) month post index procedure.
 
Efficacy will be assessed by the change in Visual Analog Scale (VAS) Nasal Symptom Score (NSS) from baseline through 3 months for rhinorrhea and nasal congestion.

Additional Evaluations:	
Additional information, as listed below, will be collected and the resulting data analyzed and reported for each follow-up, as applicable.
 
• A change in the VAS NSS from baseline.• A change in reflective Total Nasal Symptom Score (rTNSS) from baseline for rhinorrhea.• A change in rTNSS from baseline for nasal congestion.• A change in rTNSS from baseline.• A change in Postnasal Drip (PND) from baseline.• A change in Quality of Life (mini-Rhinoconjunctivitis Quality of Life Questionnaire (RQLQ) from baseline.• Procedure tolerability (e.g., discomfort, length of procedure)• Individual symptoms (e.g., post-nasal drip, nasal itching, sneezing)• Responder rates.• Patient satisfaction (e.g., patient reported symptom relief)• Endoscopic assessment.• Post-procedure discomfort (e.g., headache, facial pain, ear pain/blockage).• All adverse events regardless of severity or relatedness. 
All subjects who undergo treatment will be followed to 1 year for informational purposes and any study related findings will be reported.

Anticipated Duration:	
The study is anticipated to begin enrollment in Q1 of 2022 with enrollment complete in Q2 of 2022. The last patient visit is expected to take place by or during Q2 of 2023.

Study Evaluations:	Table 1 provides an overview of all protocol-related activities the Subject can expect to undergo as part of study participation.
Indications for Use	The NEUROMARK™ System is indicated for use in otorhinolaryngology (ENT) surgery for creation of radiofrequency (RF) lesions to disrupt posterior nasal nerves in patients with chronic rhinitis.
Intended Use:	The NEUROMARK™ System is intended for the application of Radiofrequency energy to create lesions in mucosal tissue in otolaryngological [also known as Ear, Nose and Throat (ENT)] procedures in patients with chronic rhinitis.

Screening Considerations:

- If data are available at baseline and the information collected per protocol, the existing data may be used to support patient screening. The test/assessment may not need to be redone.

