4.6.3 Immediately Pre-Treatment

A final eligibility assessment will be conducted immediately pre-treatment to confirm continued eligibility. If the subject meets all eligibility criteria the subject may undergo the NEUROMARK™ procedure on the same day that the screening assessments are performed. Once the subject completes the screening procedures and meets all eligibility criteria, the NEUROMARK™ procedure should be scheduled within 14 days unless otherwise approved by Sponsor. The following evaluations will be performed immediately prior to the study procedure. See Testing and Evaluation Guidelines (**Appendix F**) for evaluation details.

- Confirmation of no indication of COVID-19 infection at the time of treatment.
- Review of concomitant medications.
- Physical exam (height, weight, blood pressure, respiratory rate, heart rate and temperature).
- Endoscopic assessment (recorded).

Once eligibility is confirmed, Subject will be prepared for the treatment following Standard of Care (SOC) for similar procedures and per the manufacturer's IFU (**Appendix B**).

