11 STATISTICAL ANALYSIS

This is a prospective, single-arm, multicenter, safety and efficacy study.

Summary statistics will be calculated for endpoints and additional evaluations. Categorical variables will be summarized using frequency distributions and continuous variables will be summarized with means and standard deviations (normal distributions) or medians and ranges (non-normal distributions). Confidence intervals (95% CI) may be computed for select study measures.

Each subject serves as their own comparison of pre-procedure to post-procedure outcome scores. Primary efficacy will be assessed based on a reduction in the VAS Nasal Symptom Score as related specifically to rhinitis (rhinorrhea and nasal congestion) from pre-procedure [baseline] to 3 months post-procedure. The statistical methodology is targeted to employ the paired *t*-test and/or its nonparametric equivalent (the Wilcoxon Signed Rank test) with a 2-sided alpha level of 0.05. Additional Evaluations, as listed in the Protocol Synopsis, will be evaluated in a similar manner.

All subjects treated will be included in the safety analyses. All subjects treated who have at least one follow-up will be included in the efficacy analyses. All subjects treated will be included in the safety analyses.

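### The only pre-treatment VAS is both the entry test and the efficacy baseline, so regression to the mean biases the single-arm estimate towards improvement, by an amount the documents do not fix

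*Combined protocol and SAP*

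**What the plan says.** Section 4.6.2 (Active Screening), under the assessments needed to establish eligibility, has the entry "Administer Baseline VAS NSS, rTNSS, mini-RQLQ". Table 2 in Section 1.1 then sets cut-offs on that VAS: at least 5.0 for runny nose (I-E), at least 2.5 for congestion (I-F) and, in I-G, "Confirmation that the total combined VAS NSS score is ≥ 10 for nasal congestion and runny nose". I-E and I-F also set rTNSS minimums.

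The Synopsis defines efficacy as the "change in Visual Analog Scale (VAS) Nasal Symptom Score (NSS) from baseline through 3 months for rhinorrhea and nasal congestion", which are the two symptoms that gate entry. Section 11 adds "This is a prospective, single-arm, multicenter, safety and efficacy study" and "Each subject serves as their own comparison of pre-procedure to post-procedure outcome scores". On the test it says "The statistical methodology is targeted to employ the paired *t*-test and/or its nonparametric equivalent", at two-sided 0.05.

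In Table 1 the VAS NSS row is marked at Screening and next at 1 month; the Immediately Pre-treatment cell is empty. Section 4.6.3 opens with "A final eligibility assessment will be conducted immediately pre-treatment to confirm continued eligibility", but its list holds only a COVID-19 check, medications, physical exam and endoscopy. Treatment may take place on the screening day, is expected within 14 days, and may be later with sponsor approval. The Synopsis also says that, where data were collected per protocol, "the existing data may be used to support patient screening". No run-in, averaged baseline, performance goal or adjustment for regression to the mean is described.

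**The concern.** One measurement does two jobs. Among people whose symptoms vary from visit to visit, those who pass a cut-off on a given day include some who were having a worse day than usual. Their next score is lower on average even if nothing is done. When the qualifying score is also the baseline, that fall is counted as improvement. A concurrent control arm would show the same fall and cancel it, but this design has none.

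Two results are affected. The mean reduction, which is the main product of a single-arm study, is overstated, as is any responder rate built on the same baseline. The test of zero change also does not hold its stated 5% level under no device effect. The rTNSS analyses share the problem, because rTNSS also gates entry.

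**Working it through.** **What the plan gives.** It states no expected change, SD or reliability, so no figure of its own on this point can be reproduced. The sample size can: 30 × 1.20 = 36 treated (Section 11.2). The check uses n=30 and n=36.

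**Inputs from the documents.** VAS cut-offs of 5.0, 2.5 and sum 10; screening VAS as baseline; paired t-test, two-sided 0.05; no control.

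**Assumed inputs (not in the documents).** Each item scored 0 to 10; mean 5, 6 or 7 per item before selection; SD 2.0 or 2.5; visit-to-visit reliability r from 0.5 to 0.9; correlation of 0.4 between the two symptoms, in both true scores and visit errors; device effect zero. The rTNSS cut-offs were not modelled.

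**Formula.** Ignoring the ends of the scale, the expected spurious fall in the sum is

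(1 − r) × (mean sum among entrants − mean sum before selection).

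The shift of the t statistic is fall / (SD of change / √n).

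**Mid-range case (item mean 6, SD 2.5, r = 0.7).** Simulated entrants average 14.43 on the sum, against 2 × 6 = 12 before selection. The formula gives 0.3 × (14.43 − 12) = 0.73. The simulation, which caps items at 0 and 10, gives 0.78 (runny nose 0.47, congestion 0.31). With SD of change 2.88, the shift is 0.78 / (2.88 / √30) = 1.48, and the simulated rejection rate is 30%.

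**Range.** Simulated results with zero device effect and the screening score as baseline:

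| Item mean, SD, r | Entrants' mean sum | Spurious fall in sum | SD of change | Rejection n=30 | Rejection n=36 |
|---|---|---|---|---|---|
| 5, 2.5, 0.5 | 13.69 | 1.86 | 3.67 | 78% | 84% |
| 5, 2.0, 0.8 | 12.99 | 0.60 | 2.03 | 34% | 41% |
| 6, 2.5, 0.7 | 14.43 | 0.78 | 2.88 | 30% | 35% |
| 6, 2.0, 0.8 | 13.83 | 0.38 | 2.01 | 17% | 19% |
| 7, 2.0, 0.9 | 14.89 | 0.10 | 1.40 | 7% | 7% |

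If the visit errors of the two symptoms are instead uncorrelated, the falls are smaller. At mean 7 with r of 0.8 to 0.9 they are about 0.07 to 0.15 points, with 6% to 8% rejection. At mean 5 with r = 0.5 the fall is about 1.5 points, with 69% rejection. Every setting points towards improvement.

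**Effect of a second, ungated baseline.** If its error is independent of the screening error, the expected change is about 0.0 and rejection about 5%. If the errors are correlated, some of the fall stays. In the mid-range case, error correlation 0.5 leaves 0.39 points (0.39 / 0.78 = 50%) and 11% rejection; correlation 0.9 leaves 0.70 points (0.70 / 0.78 = 90%) and 25%.

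**Effect of re-applying the cut-offs to the second score.** The selection returns: the fall measured from it is still up to 1.4 points, with up to 53% rejection at n=30. If the cut-offs are not re-applied, about 6% to 40% of entrants would score below one of them on an independent repeat. The protocol therefore has to say how such a score is treated.

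**The case against.** The strongest reply is that the size is unknown and could be small. Sites may review records before approaching patients (Section 4.6.1), so the people screened may already lie well above the cut-offs; at mean 7 with high reliability, rejection is close to nominal. Several criteria also limit transient highs: at least 6 months of symptoms (I-L), no newly started, unstabilised medication (E-L), no seasonal-only rhinitis (E-V), and postponement of assessments during illness. All of this stands as a limit on the size. None of it removes selection on a noisy score.

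It is also fair that the rejection rates look dramatic because the null hypothesis is zero change in an uncontrolled study. In the mid-range case the fall is 0.78 / 14.43, about 5% of the baseline sum. The documents do not say whether the endpoint is the sum or each item, and the per-item falls are smaller.

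A reader might infer that a positive result here would be nothing more than regression to the mean. The documents do not support that: a real effect may well exceed a bias of this order. A reader might equally infer that a second baseline removes the problem entirely. It does so only if its error is independent of the screening error, and Section 4.6.3 permits same-day treatment. Recall periods would be in Appendices F and G, which were not available. A repeat VAS described only in Appendix F cannot be excluded, but it would conflict with Table 1 and need reconciling.

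**Conclusion.** The point holds. The screening VAS is the gate, the only pre-treatment score and the baseline, and in a single-arm paired comparison the resulting bias always favours improvement. That direction needs only some visit-to-visit variation and cut-offs that exclude somebody.

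The size cannot be fixed from the documents. For 0-10 items, unselected mean 5 to 7, SD 2 to 2.5 and reliability 0.5 to 0.9, the spurious fall in the two-symptom sum is about 0.1 to 1.9 points, and rejection at n=30 is about 6% to 78% against a nominal 5%. No single false-positive rate should be quoted as the plan's. Correcting the baseline would not make the change attributable to the device, since placebo response and natural history remain. It takes out, wholly or in part, a bias that is cheap to reduce before treatment and cannot be recovered afterwards.

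**What to change.** - Add VAS NSS, rTNSS and mini-RQLQ to the Immediately Pre-treatment column of Table 1 and to the list in Section 4.6.3.
- Define that score in Section 11 as the efficacy baseline, and use the screening score for eligibility only.
- State in Sections 4.6.3 and 11.1 that the VAS and rTNSS criteria are judged on the screening score. The repeat is then not an eligibility test and a lower repeat is not a deviation. Without this, the final eligibility check in 4.6.3 and the requirement in 11.1 that every treated patient be eligible would collide with sub-threshold repeat scores.
- Report two sensitivity analyses: one with the screening score as baseline, and one excluding subjects whose screening and pre-treatment scores were taken on the same day.

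The cost is a few minutes of questionnaires at a visit the subject already attends, and an amendment to Table 1 and Sections 4.6.3, 11 and 11.1. The headline reduction will probably be somewhat smaller. Removal of the bias is only partial where the two scores are close in time or their recall periods overlap.
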